### 2.1 Hypothesis and Specific Aims

We hypothesize that the addition of the AQI to AAP will (A) reduce asthma exacerbations, and (B) improve symptom control & quality of life in children with asthma. To test these hypotheses, in this study we will pursue the following specific aims:

- Aim 1: To recruit a pilot cohort of 40 children with asthma. For proof of concept, we will recruit 40 children with asthma from Children's Hospital of Pittsburgh, the only children's hospital serving southwest Pennsylvania (metropolitan area >2.6 million people). Baseline knowledge about the AQI including familiarity, usage, and prior healthcare provider discussion will be assessed.

- Aim 2: To evaluate if the addition of the AQI to AAP reduces asthma exacerbations in a pilot study of children. Participating children (Aim 1) will be randomized to one of two groups. All participants/caregivers will receive an AAP and verbal AQI education. The intervention group will additionally demonstrate the ability to check the AQI, and AQI recommendations will be incorporated onto their written AAP. Children will be followed monthly for 6 months to evaluate adherence to AQI recommendations and assess the frequency of asthma exacerbations, defined per ATS guidelines. Other known factors contributing to asthma exacerbations, such as asthma severity, viral illnesses, allergic triggers will also be monitored.
- Aim 3: To examine whether the addition of the AQI to AAP improves asthma symptom control and quality of life in a pilot study of children. Asthma symptom control will be measured in participating children monthly, and quality of life will be assessed before randomization and at 6 months. Symptom control and quality of life will be evaluated within (before/after intervention) and between groups.

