## 11. CLINICAL MANAGEMENT AND DATA COLLECTION:

Table 2: Summary of Study Protocol

VISIT	LOCATION	TIMING	QUESTIONNAIRE	MEASURES	SPECIMENS
V1	In-person, PCTRC	Start	AQI intake*, Intake, PA, ACT or CACT, PAQLQ, tobacco intake	Spirometry, FeNO, ht, wt	NEC, urine
V2	Telephone	W4, 4 wks post V3 (+/- 7d)	sRQ, AQI_f/u, PA, ACT or CACT.	-	-
V3	Telephone	W8, 4 wks post V3 (+/- 7d)	sRQ, AQI_f/u, PA, ACT or CACT.,	-	-
V4	Telephone	W12, 4 wks post V3 (+/- 7d)	sRQ, AQI_f/u, PA, ACT or CACT.	-	-
V5	Telephone	W16, 4 wks post V3 (+/- 7d)	sRQ, AQI_f/u, PA, ACT or CACT.	-	-
V6	Telephone	W20, 4 wks post V3 (+/- 7d)	sRQ, AQI_f/u, PA, ACT or CACT.	-	-
7V	In-person, PCTRC	W24, 4 wks post V3 (+/- 7d)	sRQ, AQI_f/u, PA, ACT or CACT.	Spirometry, FeNO, ht, wt	NEC, urine

Intake questionnaire (completed by parent); AQI intake- includes parent portion (completed by parent) + AQI follow up (completed by participant); PA=physical activity (parent and/or participant), ACT=asthma control test ages 12 and older (completed by participant); CACT=childhood asthma control test for ages 8-11 (completed by parent and participant); PAQLQ(s)-pediatric asthma quality of life questionnaire (completed by participant); participant tobacco intake form (completed by participant); sRQ= shortened respiratory questionnaire (completed by parent); AQI\_f/u=AQI follow up questionnaire (completed by participant).

Ht=height, wt=weight, NEC=nasal epithelial cells

\*AQI intake form should be completed prior to AQI education/intervention.

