## STATISTICAL PLAN:

Statistical Analysis: Data will be analyzed using SAS (SAS 9.4, Cary, N.C.). Baseline statistics per treatment group will be obtained. Bivariate analysis of covariates (age, sex, race/ethnicity, asthma severity, phenotype (i.e. atopic), socioeconomic status (SES), exposure to primary or secondary tobacco smoke, FeNO, use of controller medication, etc) between groups will be conducted using student t-test or Wilcoxon rank sum and Fisher's exact or Chi-square (where appropriate and based on distribution). Variables with significant differences between groups ( $P<0.05$ ) will be considered for inclusion in multivariate model selection. The effects of physical activity on the outcomes will be compared between groups. Baseline knowledge and usage of AQI will be assessed. Adherence to AQI will also be assessed and compared between groups, with potential stratification by AQI usage. Additionally, differences in weight and BMI will be assessed to evaluate if adherence to AQI promotes sedentarism and leads to increased weight gain. We will evaluate our outcomes (Aims 2 and 3) in three ways. First, we will evaluate the average difference (overall mean) between groups for our primary outcomes using T test or chi-square (where appropriate). Additionally, we will test the average mean difference between each treatment group by multivariate regression (linear for PAQLQ and ACT or CACT, and/or Poisson or logistic regression for mean asthma exacerbations depending on distribution) to allow for covariate adjustment. Second, we will use paired t-tests (or matched Wilcoxon signed-rank) to evaluate the within group effects (6 month mean – baseline) for each primary outcome. Third, to assess the effects over time in our intervention study (correlated repeat measures data), we anticipate analyzing our primary outcomes by generalized linear mixed models (GLMM). For these models, we will first evaluate the distribution of our primary outcome and determine the most appropriate link (e.g. for severe asthma exacerbations: logistic link if there are overall a high proportion of participants with none, or Poisson link if more consistent with count data). A stepwise approach will be used to build all multivariable models. All final models will include age, sex, race/ethnicity, SES, and tobacco smoke exposure. Additionally, the above outcomes will be stratified by age group (8-12y, 13-17y) to determine if the effects are greater in older children for whom the AQI recommendations may be better self-incorporated into outdoor physical activities, vs the younger group who will likely be more reliant on parental checking and activity modification.

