
Power calculations: Power calculations were conducted using G\*Power 354 and SAS (SAS 9.4, Cary, N.C.) using proc glmpower. For mean difference between treatment groups (routine vs. intervention) with sample size of 20 participants per group, two-tailed test, alpha 0.05, we will have  $\geq 90\%$  power to detect a mean difference of 1.05 between groups for mean asthma exacerbations, ACT and C-CACT, and PAQLQ. Our study will provide  $\geq 80\%$  power to detect a mean difference of 0.91. As the clinical difference for ACT is 2-3 points, we anticipate adequate power to detect a clinical difference. The estimated clinically meaningful difference in PAQLQ is 0.5, and our study may be underpowered to detect this small of difference with this analysis. For comparison within each treatment group, comparing the matched difference (end of study- baseline), using the same assumptions above, we will have  $\geq 90\%$  power to detect a mean difference of 0.76, and  $\geq 80\%$  power to detect a mean difference of 0.66. Therefore, we expect better ability to detect changes in PAQLQ within the groups than between them. For repeat measures, we estimated our power using proc glmpower using F test based on Hotelling-Lawley trace. We estimated a study allocation of 1:1, alpha 0.05, repeated measures at 1, 2, 3, 4, 5 months, lear correlation structure with base correlation 0.85 & decay rate of 1, with an estimated mean difference of 2, standard deviation of 2, which provides a  $\geq 90\%$  power for a treatment group size of 12 for overall mean and n=26 for time\*treatment.

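### The repeated-measures group size of 12 gives about 72% power on the plan's own inputs, not 90% (19 per group are needed), and the 26 for time-by-treatment is not labelled per group or total

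*Combined protocol and SAP*

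**What the plan says.** Section 2.1 (Aim 1) sets the size of the trial: "To recruit a pilot cohort of 40 children with asthma". At 1:1 allocation that is 20 per group, and the Power calculations paragraph of the Statistical Plan uses the same "sample size of 20 participants per group" for its two-group comparison.

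For repeated measures, the same paragraph uses proc glmpower with an F test based on the Hotelling-Lawley trace. Its inputs are:

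- equal group sizes and a 5% significance level;
- for the visits and their correlation, "repeated measures at 1, 2, 3, 4, 5 months, lear correlation structure with base correlation 0.85 & decay rate of 1";
- a between-group difference of 2 and an SD of 2.

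It concludes that these give at least 90% "power for a treatment group size of 12 for overall mean and n=26" for time-by-treatment.

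The analysis this supports is the third one listed under Statistical Analysis: "we anticipate analyzing our primary outcomes by generalized linear mixed models (GLMM". Table 2 in section 11 schedules six follow-ups, V2 to V7, the last at "W24, 4 wks post V3 (+/- 7d").

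**The concern.** Averaging visits that are correlated at 0.72 to 0.85 removes little variance. A difference of 2 with SD 2 is one SD at a single visit, and the visit average cannot be much more sensitive than that. A requirement of only 12 per group therefore looks too small.

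The second figure raises a different problem. It follows a figure given as a treatment group size, so the natural reading of 26 is per group, which is more than the trial will enrol. The text never says so, and it gives no pattern of means over the visits. A constant difference of 2 contains no time-by-treatment effect, so some other pattern must have been used.

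This sentence is the only power justification for the repeated-measures model. A reader would take from it that the overall-mean test has eight children per group to spare, and could not tell whether 20 per group meets the stated 90% for time-by-treatment.

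**Working it through.** **Inputs**, all from the Power calculations paragraph: average difference 2, SD 2, five visits (months 1 to 5), LEAR base 0.85 with decay 1, 1:1 allocation, alpha 0.05. The F test is non-directional.

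**Overall mean**

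1. The LEAR correlation at lag *d* months is 0.85^(1 + (*d* − 1)/3). Lags 1 to 4 give 0.85, 0.805, 0.763 and 0.7225.
2. The mean of the 5 × 5 correlation matrix is [5 + 2(4 × 0.85 + 3 × 0.805 + 2 × 0.763 + 0.7225)]/25 = 0.845.
3. The SD of a child's five-visit mean is 2 × √0.845 = 1.84. The standardised difference is 2/1.84 = 1.088, against 1.00 for a single visit.
4. With two groups the test is F(1, 2n − 2) with noncentrality n × 1.088²/2:

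| n per group | Power |
|---|---|
| 12 (plan's figure) | 72.1% |
| 17 | 86.8% |
| 18 | 88.7% |
| 19 | 90.4% |
| 20 (planned) | 91.8% |

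The plan's 12 is not reproduced. A simulation of 40,000 trials also gave 72.1% at 12 per group. With six visits the results are 72.5% at 12 and 92.0% at 20, and the first n to reach 90% is still 19.

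**Other readings at 12**

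- One-sided test: 83%.
- First-order autoregressive correlation 0.85: 75%.
- Compound symmetry 0.85: 70%.
- 12 as a total (6 per group): 40%.
- Times entered in weeks: 86%.
- The 2 read as a variance: 94.9%, with 10 per group sufficient. This contradicts the printed standard deviation.

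Reaching 90% at 12 needs a standardised difference of 1.385. That means an average difference of 1.385 × 1.84 = 2.55, or an SD of 1.57, or a common correlation of about 0.40.

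**Comparison within the paragraph.** The between-group claim (difference 1.05, 20 per group, at least 90%) reproduces at 89.9% if the SD is 1. The plan does not state that SD. On that basis 1.05 SD needs about 20 per group, so an effect of 1.09 SD cannot need only 12.

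**Time-by-treatment**

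The visit profile is not given, so the 26 can be neither confirmed nor refuted. What can be computed is the power at 20 per group if the 26 is taken as correct. The test is Hotelling's T² on four visit contrasts, F(4, 2n − 5), with noncentrality proportional to n. The result does not depend on which profile was used.

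| Reading of 26 | Power at 20 per group |
|---|---|
| Per group, exactly 90% at 26 | 78.1% |
| Per group, upper bound (90% already at 25) | 80.1% |
| Per group, six visits (five contrasts) | 77.5% |
| Total (13 per group) | 99.2% |

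One profile that fits the per-group reading is a linear difference rising from 1.17 to 2.83, which averages 2.

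**Dropout.** The plan states no rate. Assumed losses of 10% and 15% leave 18 and 17 per group. Overall-mean power is then 88.7% and 86.8%. Time-by-treatment power on the per-group reading is 72% and 69%.

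**The case against.** The strongest objection is that the plan never says how the difference of 2 runs over the visits, so the 12 may be right and the description of the effect wrong. A linear profile from about 1.7 to 3.4 gives 12 per group for the overall mean and 25 for time-by-treatment, close to both printed figures. That profile averages 2.55, however, not 2. The overall-mean test depends only on the average, so every profile averaging 2 gives the same 72.1%. If 2 were only the final-visit difference, the requirement would rise: a linear rise from 0 to 2 needs 73 per group. The cause of the error is therefore open, but the sentence is wrong as written. The same holds for the variance reading: it would explain a small n, but it would itself be an error in the text.

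Three further points stand in part.

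- The comparison with the 1.05 figure rests on an inferred SD of 1, so it is supporting evidence only.
- The 26 is not a proven error. It lacks a label and a profile, and the shortfall is conditional on the per-group reading.
- The practical effect on the overall-mean test is small. The trial is a pilot with its size fixed at 40, and the planned model may be logistic or Poisson with covariates, which a Gaussian two-group calculation only approximates. A difference of a point or two in power should not be over-read, but the gap between 72% and 90% is far larger than that.

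**Conclusion.** The concern holds. The claim of at least 90% power at 12 per group is wrong on the stated inputs, taking 2 as the visit-averaged difference: power is about 72%, and 19 per group are needed. The planned 20 per group still gives about 92%, so the test itself is not compromised. What is misstated is the margin, which is one child per group before any dropout.

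The 26 cannot be interpreted as printed. If it is per group, the trial is smaller than its own stated requirement, and time-by-treatment power is about 78% (at most about 80%). If it is a total, power is about 99% and there is no shortfall. The error in the 12 is established with high confidence; how it arose cannot be determined from the documents.

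**What to change.** - Rerun the repeated-measures calculation at 20 per group with the six scheduled follow-ups (W4 to W24).
- State the visit-by-visit mean profile and whether 2 is the average or the final difference. If another input was actually used, such as a different SD or average difference, correct that input.
- Replace the 12 and the 26 with the power obtained at 20 per group. For the overall mean this is about 92% if the difference averages 2 and the SD is 2.
- Label every n as per group or total.
- If time-by-treatment power falls below the stated 90%, say so and treat that test as exploratory.

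The cost is one rerun and one rewritten sentence. It needs no extra patients and no design change. The only consequence is that the stated figures become less favourable.
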